### GCP Statement

This study will be conducted in accordance with the United States (US/USA) Food and Drug Administration (FDA) and International Conference on Harmonization (ICH) guidelines on current Good Clinical Practice (GCP) in accordance with the ethical principles that have their origin in the Declaration of Helsinki, and relevant country-specific regulatory requirements of the country in which the research will be conducted.

## 2. SYNOPSIS

Name of Sponsor/Company: Fibrocell Technologies, Inc. (Fibrocell)		
Name of Investigational Product: FCX-013 + veledimex (FCX-013 plus veledimex)		
Name of Active Ingredient: FCX-013 (Genetically Modified Autologous Human Dermal Fibroblasts) Veledimex capsules for oral administration		
Protocol Number: FI-SC-001	Phase: 1/2	Country: USA
Title of Study: A Phase 1/2 Study of a Combination of FCX-013 (Genetically-Modified Autologous Human Dermal Fibroblasts) Plus Veledimex for the Treatment of Moderate to Severe Localized Scleroderma (Morphea)		
Study center(s): Up to 3 centers		
Studied period (years): Estimated date first subject screened: 4Q2019 Estimated date last subject completed: 2035 (includes long-term follow-up)		Phase of development: I Phase 1/2
Objectives: Primary: The primary objective of this protocol is to evaluate the safety of FCX-013 plus veledimex in subjects with moderate to severe localized scleroderma/morphea. Secondary: The secondary objective of this protocol is to evaluate the antifibrotic effects of FCX-013 plus veledimex via the LoSCAT (Localized Scleroderma Assessment Tool) and durometry.		
Methodology: This is an open-label, single arm Phase 1/2 study being conducted by Fibrocell to evaluate FCX-013 in subjects with moderate to severe localized scleroderma. Approximately ten subjects will be enrolled and receive FCX-013. The study is divided into the following periods: Screening (including Manufacturing of FCX-013), Treatment, and Long-Term Follow-Up. The Screening Period consists of evaluation of eligibility, the collection of one set of three 3-4 mm biopsies for the manufacture of FCX-013 product, and the identification of potential target sclerotic lesions. Due to the FCX-013 manufacturing process, the Screening Period is expected to have a duration of approximately 4-6 months; however, this period can be extended to accommodate subject scheduling, variations in manufacturing duration and protocol mandated delays (i.e. pauses due to staggered treatment).		


After FCX-013 manufacturing is complete, Fibrocell (the Sponsor) and the Investigator will mutually agree on the planned date for injection of FCX-013.
 
The Treatment Period will have a 2-week duration. One administration of FCX-013 will consist of a maximum of 4 mL of FCX-013 administered in up to sixteen (16) 0.25 mL intradermal injections. On Day 1, FCX-013 will be intradermally injected, using a retro-tracing technique, into the sclerotic lesion targeted for treatment. On Day 1, following the injection of FCX-013, subjects will initiate a 14-day course of veledimex to be taken orally daily.
 
Administering FCX-013 following each of the first three subjects requires that the previous subject complete Week 4 evaluations, and that the Investigator(s) must have received approval from the Data Safety Monitoring Board (DSMB).
 
The End of Treatment visit is at Week 12.
 
Safety and clinical efficacy evaluations are conducted throughout the study. Safety will be assessed through adverse events (AEs), physical examinations, vital signs, clinical laboratory evaluations, electrocardiograms (ECGs) and concomitant medications.
 
The Long-Term Follow-Up period is an approximately 15-year period following the End of Treatment in which safety is monitored annually.

Number of subjects (planned): Approximately 10

Diagnosis and main criteria for inclusion: Adults with a clinical diagnosis of any subtype of moderate to severe localized scleroderma/morphea with sclerotic lesions.

Investigational product, dosage and mode of administration:
 

• FCX-013 via intradermal injection

• Veledimex capsule for oral administration

 
One administration of FCX-013 will consist of a maximum of 4 mL of FCX-013 administered in up to sixteen (16) 0.25 mL intradermal injections. On Day 1, FCX-013 will be intradermally injected, using a retro-tracing technique, into the sclerotic lesion targeted for treatment. On Day 1, following the injection of FCX-013, subjects will initiate a 14-day course of veledimex to be taken orally daily.

Reference therapy, dosage and mode of administration: Not applicable.


Criteria for evaluation:
 
Safety: Safety will be assessed through AEs, physical examinations, vital signs, clinical laboratory evaluations, ECGs, and concomitant medication use. Analysis of replication-competent lentivirus (RCL) antibodies will also be performed.
 
Efficacy: Clinical evaluation of antifibrotic effects via durometry evaluation and LoSCAT (Localized Scleroderma Assessment Tool).

**Quality of life** will be assessed using the SkinDex 29+3.

**Statistical methods:**

Descriptive statistics are planned for this study.

**Safety:**

Safety evaluations will be based on listed AEs, physical examinations, vital signs, clinical laboratory evaluations, ECGs and prior/concomitant medications, and assessment for the presence of RCL antibodies. The AE severity will be described using National Cancer Institute (NCI) Common Terminology Criteria for Adverse Events (CTCAE) grades, using the current version at study start. AEs will be coded using the Medical Dictionary for Regulatory Activities (MedDRA; version 23.0 or later) and described by body system and preferred term, relationship to FCX-013, seriousness, and severity. AEs causing investigational product discontinuation and/or early study discontinuation, and serious adverse events (SAEs) will be noted.

**Efficacy:**

All subjects who were administered FCX-013 and had at least one assessment of the target lesion post-administration will be included in the efficacy population.

The change from baseline in the LoSCAT and durometry scores will be reported descriptively, as will changes in the SkinDex 29+3 scores.

The primary method of handling data will be last observation carried forward (LOCF).

#### 4. LIST OF ABBREVIATIONS

Abbreviation	Definition
AE	Adverse Event
ALT/SGPT	Alanine Aminotransferase
AST/SGOT	Aspartate Aminotransferase
CFR	Code of Federal Regulations
CRF	Case Report Form
CTCAE	Common Terminology Criteria for Adverse Events
DSMB	Data Safety Monitoring Board
ECG	Electrocardiogram
EDC	Electronic Data Capture
FAS	Full Analysis Set
FCX-013	Genetically-Modified Autologous Human Dermal Fibroblasts (product -013)
FDA	Food and Drug Administration
GCP	Good Clinical Practice
Hep B	Hepatitis B
Hep C	Hepatitis C
HIPAA	Health Insurance Portability and Accountability Act
HIV	Human Immunodeficiency Virus
IB	Investigator's Brochure
ICF	Informed Consent Form
ICH	International Conference on Harmonization
IP	Investigational Product
IRB	Institutional Review Board
LOCF	Last Observation Carried Forward
MCH/MCHC/ MCV	Mean Corpuscular Hemoglobin/ Hemoglobin Concentration/Volume
MedDRA	Medical Dictionary for Regulatory Activities
MMP	Matrix Metalloproteinase
NCI	National Cancer Institute
PCR	Polymerase Chain Reaction
PI	Principal Investigator
PP	Per Protocol
qPCR	Quantitative Polymerase Chain Reaction
RBC	Red Blood Cell(s)
RCL	Replication-Competent Lentivirus
RDW	Red Cell Distribution Width
SAE	Serious Adverse Event
Sub-I	Sub-Investigator
TEAE	Treatment-Emergent Adverse Events
US/USA	United States of America
WBC	White Blood Cell(s)
WHODrug	World Health Organization Drug Global Dictionary

## 5. INTRODUCTION

### 5.1. Background: Localized Scleroderma/Morphea

Localized scleroderma/morphea is an autoimmune inflammatory sclerosing disorder of cutaneous induration that can cause permanent functional disability and disfigurement. This rare fibrosing disorder of the skin and underlying tissues is distinct from systemic sclerosis and encompasses several subtypes classified by the depth and pattern of lesion(s). The underlying pathogenesis of localized scleroderma is not completely understood but is likely multifactorial, involving genetic factors and environmental exposures, culminating in small vessel damage, release of profibrotic cytokines, and ultimately leading to disruption of the balance between collagen synthesis and destruction. The incidence and prevalence of localized scleroderma is poorly described. The incidence of localized scleroderma has been estimated as approximately 0.4 to 2.7 per 100,000 individuals. (Fett, 2011 Part 1; Peterson, 1997). Prevalence of localized scleroderma is approximately 50 per 100,000 individuals (Browning, 2013). The prevalence is similar in children and adults (Peterson, 1997, Leitenberger, 2009).

Overproduction and accumulation of collagen is a hallmark of the disease. Given the increased levels of collagen, a biological approach to break down and inhibit collagen synthesis by a matrix metalloproteinase (MMP) is a novel therapeutic approach for the treatment of localized scleroderma.

The assessment of disease activity and depth of involvement guides therapeutic decision-making in localized scleroderma/morphea. Because of the self-limited nature of localized scleroderma/morphea, patients with limited plaque disease may elect to defer therapy. For patients with superficial (dermal) circumscribed disease who desire treatment, but do not have access to or prefer to avoid the frequent visits required for phototherapy, treatment options include high potency topical corticosteroids, intralesional corticosteroids, a topical vitamin D analog, topical tacrolimus, or imiquimod. For patients with superficial (dermal) forms of morphea who are able to receive phototherapy, treatment with UVA1 is preferred; alternatives include broad-band UVA, narrow-band UVB, or PUVA. Phototherapy is unlikely to be effective for localized scleroderma/morphea involving the subcutaneous tissue, muscle, or bone. Rapidly progressive, severe, disabling disease requires systemic therapy, involving a combination of methotrexate and systemic corticosteroids. Localized scleroderma/morphea may cause joint contractures and other functional impairments secondary to deep tissue sclerosis. All patients should be clinically assessed for the development of these findings. Physical therapy is essential for patients at risk for or who show evidence of functional impairments.

The risk-benefit assessment of pursuing treatment for localized scleroderma lesions depends on the potential for functional impairment and symptom burden due to sclerotic lesions.

## **5.2. Study Rationale**

Fibrocell is developing a two-component therapeutic consisting of FCX-013 and veledimex for the treatment of localized scleroderma (morphea) by resolving fibrotic lesions and normalizing dermal collagen production. The first component, FCX-013, is genetically-modified autologous human dermal fibroblasts that have been engineered with a lentiviral vector to express MMP-1 under the control of a RheoSwitch (RTS®) system. The lentiviral vector-containing gene constructs for MMP-1 and the RTS® is referred to as LV-RTS-MMP-1 (or INXN-2005). The second component, veledimex, is a small molecule which activates the RTS to induce expression of MMP-1. The FCX-013 product is administered by intradermal injection, and veledimex is administered orally in a liquid filled gelatin capsule formulation.

The clinical trial will be conducted in compliance with the protocol, Good Clinical Practice (GCP), and applicable regulatory requirements.

## **6. TRIAL OBJECTIVES AND ENDPOINTS**

### **Primary Objective**

The primary objective of this study is to evaluate the safety of FCX-013 plus veledimex in subjects with moderate to severe localized scleroderma/morphea.

### **Secondary Objective**

The secondary objective of this study is to evaluate the antifibrotic effects of FCX-013 plus veledimex via durometry and the LoSCAT (Localized Scleroderma Assessment Tool).

**Safety evaluations** include assessment of treatment-emergent adverse events (TEAEs), including serious adverse events (SAEs); change in clinical laboratory values; change in vital signs; change in electrocardiograms (ECGs); and incidence of replication-competent lentivirus (RCL) antibodies.

**Efficacy endpoints** include the change from Baseline in the durometer score and LoSCAT score.

## **7. INVESTIGATIONAL PLAN**

### **7.1. Overall Study Design**

This is an open-label, single arm Phase 1/2 study being conducted by Fibrocell to evaluate FCX-013 in subjects with moderate to severe localized scleroderma/morphea. Approximately ten subjects will be enrolled and receive FCX-013.

The study is divided into the following periods: Screening (including Manufacture), Treatment, and Long-Term Follow-Up. The Screening Period consists of entry criteria evaluations, the collection of one set of three 3-4 mm biopsies for the manufacture of FCX-013 product, and the identification of potential target sclerotic lesions. Due to the FCX-013 manufacturing process, the Screening Period is expected to have a duration of approximately 4-6 months; however, this period can be extended to accommodate subject scheduling, variations in manufacturing duration and protocol mandated delays (i.e. pauses due to staggered treatment).

After FCX-013 manufacturing is complete, Fibrocell (the Sponsor) and the Investigator will mutually agree on the planned date for injection of FCX-013.

The Treatment Period will have a 12-week duration. One administration of FCX-013 will consist of a maximum of 4 mL of FCX-013 administered in up to sixteen (16) 0.25 mL intradermal injections. On Day 1, FCX-013 will be intradermally injected, using a retro-tracing technique, into the sclerotic lesion targeted for treatment. On Day 1, following the injection of FCX-013, subjects will initiate a 14-day course of veledimex to be taken orally daily. During the Treatment Period, subjects will be evaluated at Weeks 2, 4, and 12, and have an end-of-treatment visit at Week 12.

Treatment with FCX-013 will be staggered for the first three subjects. Administering FCX-013 following each of the first three subjects requires that the previous subject complete Week 4 evaluations, and that the Investigator(s) must have received approval from the Data Safety Monitoring Board (DSMB).

Safety and clinical efficacy evaluations are conducted throughout the study. Safety will be assessed through adverse events (AEs), physical examinations, vital signs, clinical laboratory evaluations, ECGs and concomitant medications.

The Long-Term Follow-Up period is an approximately 15-year period following End of Treatment in which an examination of injection sites is conducted, and safety is monitored annually, at a minimum.

### **7.2. Number of Subjects**

The enrollment target is approximately 10 subjects.

### **7.3. Treatment Assignment**

This is an open label study. All subjects will receive a combination of FCX-013 plus veledimex. Upon screening, the subject will be assigned a unique Subject Number. Subjects who are eligible for participation will retain the same Subject Number for the duration of the study. Subjects who

satisfy all the inclusion and none of the exclusion criteria will enter a screening period prior to injection(s) with FCX-013 and veledimex administration.

#### **7.4. Randomization and Blinding**

This is an open-label, single-arm study. No randomization or blinding techniques will be utilized.

#### **7.5. Dose Adjustment Criteria**

##### **7.5.1. Safety Criteria for Adjustment or Stopping Doses**

An objective of this study is to generate a safety profile of FCX-013 plus veledimex in subjects with moderate to severe localized scleroderma/morphea. To minimize risk, cumulative safety data will be reviewed by the Medical Monitor. Events that will result in immediate enrollment discontinuation and treatment discontinuation for all subjects are a positive RCL assay and histologically confirmed cancer in combination with the presence of viral vector in the tumor. In addition, the Medical Monitor may interrupt study dosing and/or study entry at any time if medically indicated.

Occurrence of any of these observations will trigger a temporary suspension of FCX-013 plus veledimex administration pending a safety investigation:

- A treatment emergent SAE or suspected SAE related to FCX- 013, the FCX-013 administration procedure, veledimex administration or any other protocol procedure.
- A positive RCL quantitative polymerase chain reaction (qPCR) assay result. A positive RCL qPCR assay will result in suspension of FCX-013 administration. The result will be confirmed by conducting a biological-based assay. If both assays are positive, FCX-013 administration will be discontinued and no further enrollment into the study will be allowed.
- An autoimmune response determined by the Investigator to be possibly, probably or definitely related to treatment.
- Any systemic infection designated as suspected to be related to FCX-013.
- A treatment emergent uncontrolled bacterial, viral, or fungal infection in a lesion that was administered by investigational product (IP) where product sterility testing results reported post injection were positive for contamination.
- Any subject diagnosed with a histologically proven skin cancer (including sarcomas) will be biopsied and assayed for viral vector by qPCR. A positive result for viral vector will cause product administration to be suspended.
- Abnormal laboratory value(s) or clinically significant change from screening/baseline that pose a risk to safe participation.
- Abnormal test procedure result(s) or clinically significant change from screening/baseline that pose a risk to safe participation (e.g., Grade 2 or above Common Terminology Criteria for Adverse Events/CTCAE criteria (v.4.03) for ECG test).

For subject safety, investigators should continue to follow subjects in accordance with study visits and procedures as outlined in the protocol. An occurrence of any of these safety observations will be shared with all study Investigators, DSMB and the appropriate regulatory authorities. The DSMB will review the results of the safety investigation and may request any additional data needed to assess the safety of restarting product administration. The DSMB will determine if the suspension can be lifted or if the trial will need to terminate based on their review of the safety investigation.

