#### **7.7. Safety Oversight: Data Safety Monitoring Board**

A DSMB will be comprised of two clinicians with expertise in dermatology and/or scleroderma, and a statistician. The DSMB will facilitate the management and identification of potential safety concerns that could affect the safety of study subjects and will evaluate the overall progress of the study through the Treatment Period. To minimize risk, cumulative safety data will be reviewed by the DSMB. Principal investigators (PIs), additional sub-investigators (Sub-Is) and scientific personnel may participate in reviews, as appropriate.

The DSMB has the authority to recommend dose or regimen modifications for safety concerns and will provide recommendations about stopping or continuing the trial. To contribute to enhancing the integrity of the trial, the DSMB may also formulate recommendations relating to the selection/recruitment/retention of subjects, their management, improving adherence to protocol-specified regimens and retention of subjects, and the procedures for data management and quality control.

Details regarding the DSMB, procedures, responsibilities, membership, meeting intervals and data to be evaluated will be further described in the study specific DSMB Charter. A written summary documenting the results and recommendations of each DSMB meeting will be maintained on file with the Sponsor.

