**Table 4: Schedule of Events (Continued)**

**\*include height and weight at Baseline**

**An unscheduled visit, with necessary assessment, may occur as needed.**

Notes:

- a) For any subject who is diagnosed with or dies of a new malignancy, attempts will be made to collect a biopsy of the neoplastic tissue or pertinent autopsy tissue to perform relevant RCL testing.
- b) For any subject with a malignant growth in a region of FCX investigational gene therapy administration, attempts will be made to collect a skin biopsy of the malignant tissue for viral vector presence and potentially clonality of vector integration testing, as available.
- c) In years 1-5 only, a skin biopsy from the region of FCX investigational gene therapy administration (i.e., treated skin area) may be taken to test for relevant transgene and vector persistence *in subjects who consent to the collection of the biopsies required to perform the assay*. However, collection of biopsies will stop if transgene and vector persistence is undetected.

**\*Long-term Follow-Up for years 2-15 may be performed by contacting the subject to review/record requested information, ideally scheduled to follow annual visits and assessment (including relevant laboratory analyses) performed by the subject's health care provider.**

1. Report exposure to mutagenic agents and other medicinal products.
2. Report adverse events of special interest and emergence of new clinical conditions, including, but not limited to: new malignancy, new incidence or exacerbation of a pre-existing neurologic disorder, new incidence or exacerbation of a prior rheumatologic or other autoimmune disorder, new incidence of a hematologic disorder, unexpected illnesses and hospitalization(s).
3. Collection and analysis of a blood sample to monitor for RCL may be performed yearly for up to 15 years. If all post-treatment RCL assays are negative through one year following subject's final investigational product administration, collection of the yearly follow-up samples may be discontinued.

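### Protocol Section 7.5.1 gives vector-positive skin cancer two different consequences: a final stop of enrollment and treatment, and a suspension that the DSMB may lift

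*Protocol*

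**What the plan says.** Section 7.5.1 opens by naming the events that end enrollment and dosing for everyone: "Events that will result in immediate enrollment discontinuation and treatment discontinuation for all subjects are a positive RCL assay and histologically confirmed cancer". The cancer event is qualified as "histologically confirmed cancer in combination with the presence of viral vector in the tumor".

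A bullet list follows, introduced by: "Occurrence of any of these observations will trigger a temporary suspension of FCX-013 plus veledimex administration pending a safety investigation". One bullet covers a histologically proven skin cancer, sarcomas included, with a biopsy tested for vector by qPCR. It ends: "A positive result for viral vector will cause product administration to be suspended". Neither the lead-in nor this bullet mentions enrollment.

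The RCL bullet in the same list is built differently. A positive qPCR suspends FCX-013, a biological assay is used to confirm it, and then: "If both assays are positive, FCX-013 administration will be discontinued and no further enrollment into the study will be allowed".

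The section's closing paragraph covers what happens after the safety investigation: "The DSMB will determine if the suspension can be lifted or if the trial will need to terminate". Section 7.7 describes the board's role in general terms: "The DSMB has the authority to recommend dose or regimen modifications for safety concerns and will provide recommendations about stopping or continuing the trial". Note b to Table 4 says that, for a malignant growth in the treated region, "attempts will be made to collect a skin biopsy of the malignant tissue for viral vector presence". That note and the skin assessment text in Section 10.3.4 provide for the test but attach no consequence to its result.

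**The concern.** The same finding, a skin cancer carrying the vector, appears to lead both to a mandatory final stop and to a reversible pause. Safety is the primary objective (Section 6), the product is made with a lentiviral vector (Section 5.2), and this is one of only two events that the opening paragraph treats as ending enrollment and dosing. If it happened, the sponsor, the DSMB, the IRB and the investigators could each cite Section 7.5.1 for a different action.

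The subjects concerned are those not yet enrolled, those enrolled and waiting for product, and those still taking veledimex. Section 9.2 gives FCX-013 in a single session on Day 1 and veledimex for 14 days. Under the bullet alone, nothing written would stop a site from consenting new subjects and taking manufacturing biopsies (Sections 10.2.1 and 10.3.6) during the investigation.

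**Working it through.** No arithmetic applies: the check is a comparison of texts.

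**Step 1. Is it the same event?** The opening paragraph requires histological confirmation of cancer and vector in the tumor. The bullet requires histological proof of skin cancer and a positive vector qPCR. Skin cancer is a kind of cancer, so a case that meets the bullet also meets the opening paragraph in full. This takes the biopsy in the bullet to be of the tumor, as Section 10.3.4 and note b to Table 4 indicate.

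**Step 2. The two consequences side by side.**

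| | Opening paragraph | Skin cancer bullet, lead-in and closing paragraph |
|---|---|---|
| Dosing at first | Stopped for all | Suspended |
| Enrollment | Closed at once | Not mentioned |
| Duration | Final | Temporary, pending investigation |
| Who may reverse it | Nobody named | The DSMB |

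The rows on enrollment, duration and reversal differ. The first row does not differ in practice.

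**Step 3. Can the two be reconciled?**

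- *As two steps, suspension first and discontinuation after.* This works for RCL, because a second assay has to report before the final stop applies. For skin cancer the bullet's trigger is already the complete trigger of the opening paragraph, which says the stop is immediate. Nothing remains to be established between the two steps, and the bullet states no second one.
- *As a joint condition, RCL and cancer together.* The opening paragraph speaks of events in the plural, and the RCL bullet discontinues on two positive RCL assays without any cancer. The joint reading fails.
- *By precedence stated elsewhere.* The closing paragraph of Section 7.5.1, Section 7.7, note b to Table 4 and Section 10.3.4 contain no rule on which text prevails.

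**Step 4. The RCL wording.** The opening paragraph refers to a positive RCL assay without saying that it must be confirmed. The RCL bullet and Section 10.3.8 both require confirmation by a biological assay. Here the intended rule can be recovered from the text, so this is only a clarification.

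**The case against.** The strongest reply is that the section has a workable structure: the bullets give the first response and the opening paragraph gives the end state. The cancer bullet describes no second assay, so it needs no escalation sentence, and its silence need not displace the opening paragraph. The DSMB's power is to lift a suspension, which by its terms does not reach a discontinuation. Section 7.7 gives the board authority to recommend and defers detail to a charter not shown here. The Medical Monitor may also interrupt dosing or study entry at any time.

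Part of this stands. A careful team could well treat the opening paragraph as governing, and several safeguards lie between the event and any further dosing. But the text does not say that it governs. The bullet places this event in the list of suspensions, and the closing paragraph makes those suspensions reversible. The Medical Monitor's power is discretionary. A charter can describe how the board works, but the protocol would still contain both rules.

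It is also fair to say that the fix makes one positive vector qPCR final, whereas RCL needs two positive assays, and that note b contemplates clonality testing. The opening paragraph already sets that rule, however. A confirmation step would be a new decision for the sponsor.

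Three stronger inferences are not supported:

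- A reader might infer that dosing could simply continue after such a tumor. It could not: both texts halt it, and resuming needs an investigation and a DSMB decision.
- A reader might derive a count from the stagger in Section 7.1. Suppose 10 subjects, one released per gate, no DSMB review time, and the event in subject 1. With Week 4 visits on Day 29, injections fall on Days 1, 1 + 28 = 29 and 29 + 28 = 57, and subject 4 is released on Day 57 + 28 = 85. Just before Day 85, 10 − 3 = 7 subjects are uninjected. With visits on Day 24, subject 4 is released on Day 1 + 3 × 23 = 70. No gate is stated after that, so the count could be 0 by Day 85. The figure reflects the assumed timing, for which the protocol gives no basis.
- A reader might infer that veledimex would continue after confirmed RCL, because that bullet names only FCX-013. The lead-in covers both components, and the opening paragraph discontinues treatment as a whole.

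**Conclusion.** The inconsistency is real and lies in a stated safety stopping rule; it is not detail left for another document. Its reach is narrow: whether the stop after a vector-positive skin cancer is final, and whether enrollment closes. It has practical effect only while someone remains to be enrolled or injected, or is within the 14-day veledimex course. Once all subjects have been treated it changes no dosing. No number of affected subjects can be given. The conclusion rests on the protocol text alone, since the DSMB charter is not available. Severity: should-fix.

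**What to change.** 1. In the skin cancer bullet of Section 7.5.1, replace the last sentence with: *A positive result for viral vector will result in discontinuation of enrollment and of treatment (FCX-013 and veledimex) for all subjects, as stated above.*
2. In the closing paragraph of Section 7.5.1, add that the DSMB's power to lift a suspension does not apply to the events in the opening paragraph, namely vector-positive cancer and confirmed RCL.
3. Minor: in the opening paragraph, specify a positive RCL qPCR assay confirmed by the biological-based assay, to match the RCL bullet and Section 10.3.8.

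Removing the event from the opening paragraph would also end the contradiction, but it would weaken a safety rule that the protocol already states, so it is not the recommended repair.

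The cost is a wording amendment with IRB approval (Section 14.5). The trigger stays as it is, and no visit, sample, assay or CRF field is added. The DSMB loses discretion to restart after this event, which the opening paragraph already excludes.
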